### e. Sample Size Estimate

Determining a sample size based on available data is limited by the available studies on long-term outcomes including neurodevelopmental impairments or death in term and late preterm infants who have cardiovascular instability and require cardiovascular support. This sample size is based on the best available data, which is closest to the population proposed to study. Based on previous data, the incidence of death or any neurodevelopmental impairment (permanent hearing loss, blindness, moderate or severe cerebral palsy or Bayley MDI or PDI scores <70) was 32% in a similar population of critically ill newborn infants with respiratory distress and in need of mechanical ventilation, but excluding congenital diaphragmatic hernia defects. Based on 4 additional studies in similar populations of term and late preterm infants with respiratory failure, the average incidence of death or any neurodevelopmental impairment was 30%. If these studies had all included mild impairment the event rate would have been higher.

The trial is powered at 80% to detect a reduction in the primary outcome of death or any neurodevelopmental impairment at 22-26 months from 30% to 20%, for a relative risk reduction of 33%, and a relative risk of 0.67, using a two tailed test with 5% Type I error. Allowing for 10% attrition, the required sample size for this scenario is 646 (Table 10). This sample size will also provide >80% power to detect treatment differences in important secondary outcomes of days in the NICU, intubated and on a ventilator and hours on inotropes without adjusting for multiple comparisons (Table 11)."

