**Table 10. Enrollment/time/consent estimates**

Reduction in death or neurodevelopment delay at 22-26 mo	Total enrollment (including 10% loss)	Months to complete enrollment if consent rate 60%	Months to complete enrollment if consent rate 70%
10%	646	48	41

Because of the lack of data on outcomes in this population with which to ascertain power calculations with high confidence, the overall event rate of any NDI or death in this population will be calculated either: 1 year after the first patient is evaluated at 22-26 month follow-up or after 30% of a planned enrollment of 646; whichever occurs first. At this point, the number needed to achieve 80% power, to detect a difference of 10% with an alpha of 0.05 and a 2 sided t-tail test, will be recalculated.

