#### **g. Available Population**

With all NRN Centers enrolling into the observational study (which also excluded those with major congenital heart disease, acute hypotension resulting directly from known acute maternal and/or fetal hemorrhage within 24 hours prior to delivery, pituitary hypoplasia, congenital adrenal hyperplasia, or known chromosomal disorder), ~100-115 mechanically ventilated infants in this gestational age range are admitted to NRN Centers each month and 25% of these received inotropes (21% if exclude encephalopathy, CDH, and omphalocele and those who receive cooling for HIE). We, therefore, anticipate ~22 to 25 eligible infants each month.

Infants in the same age group within the NRN with hypoxic ischemic encephalopathy may be eligible for the ongoing cooling studies in the NRN. However, infants who are cooled or have HIE will be ineligible for this study.

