Serious adverse events to be reported to NICHD within 24 hours include death, late onset sepsis, hyperglycemia receiving insulin, hypertension receiving antihypertensive medication or intestinal perforation with an assessment as best as possible as to the cause of the perforation (NEC, spontaneous, other).

b. Interim safety monitoring

The DSMC will compare the incidence of death and a composite of serious adverse events including death, late onset sepsis, intestinal perforation, and hyperglycemia requiring insulin between the two treatment arms after every 100th infant reaches status (death, discharge, transfer or 60 days of age). Since 646 infants are to be enrolled in this trial, this will involve interim looks approximately once every 9 months, or after the enrollment of every additional 160 infants, giving a Pocock boundary of 2.413, with a corresponding significance level of  $p<0.0158$  (Pocock, 1977). Such reports will be forwarded to the Chair of the DSMC when there is any suggestion of a trend towards a difference between the two treatment arms emerging. They will also be made available to the full DSMC at their scheduled meetings after 50% and 75% of the trial infants reach status as defined by the GDB. Interim efficacy analysis using O'Brien-Fleming stopping bounds will also be made available to DSMC when 50% of primary outcome data is available.

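### The safety boundary of 2.413 belongs to five equally spaced looks, but the stated rule of a look every 100 infants gives six or seven, and the three look schedules cannot all hold

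*Combined protocol and SAP*

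**What the plan says.** Section 8, DSMC Safety Monitoring, item b (Interim safety monitoring), sets the rule first: death and a composite of serious adverse events are compared "between the two treatment arms after every 100th infant reaches status (death, discharge, transfer or 60 days of age". The next sentence, presented as what this means for 646 infants, says "this will involve interim looks approximately once every 9 months" and then "or after the enrollment of every additional 160 infants, giving a Pocock boundary of 2.413", with a nominal significance level of p<0.0158. The paragraph does not give the number of looks or an overall alpha for safety, and it does not say whether a final analysis counts as a look. It adds that reports go to the DSMC Chair if a trend is suspected, and to the full committee at meetings once 50% and 75% of infants have reached status.

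Three other places matter. Section 7e states the type I error for the primary outcome only: "using a two tailed test with 5% Type I error". Section 7g gives accrual: "We, therefore, anticipate ~22 to 25 eligible infants each month". Table 10 gives 48 months of enrollment at 60% consent and 41 months at 70%. The text below Table 10 plans to recalculate the sample size from the overall event rate: "At this point, the number needed to achieve 80% power, to detect a difference of 10% with an alpha of 0.05".

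**The concern.** Two consecutive sentences describe different monitoring plans, yet the second is written as a consequence of the first. Steps of 100 infants do not become steps of 160. The clock also changes, from infants who have reached status to infants enrolled. A Pocock constant depends on the number and spacing of looks, so a single printed constant cannot fit every schedule in the paragraph.

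This is the only numerical threshold the plan gives for comparing deaths and serious adverse events between arms. If it does not match the schedule that is run, its overall error is not the one intended. Two statisticians following the text faithfully could also give the DSMC reports at different times, in different numbers, against the same boundary.

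**Working it through.** **Inputs.** Planned enrollment is 646, and the three schedules and the boundary are as stated in Section 8b. Accrual is 22 to 25 eligible infants per month (Section 7g) at 60% to 70% consent (Table 10). Enrollment lasts 48 or 41 months (Table 10). The overall two-sided 5% is an assumption for safety, borrowed from the primary outcome in Section 7e.

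**Reproducing the plan's figure.** The two-sided p-value of z = 2.413 is 2 × [1 − Φ(2.413)] = 0.0158, so the two printed numbers agree with each other. The Pocock constant c for K looks solves P(|Z_k| ≥ c at any look k = 1,…,K) = 0.05, where Corr(Z_j, Z_k) = √(n_j/n_k) for j < k. Recursive numerical integration with equal spacing gives:

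| K | c | nominal p |
|---|---|---|
| 4 | 2.361 | 0.0182 |
| 5 | 2.413 | 0.0158 |
| 6 | 2.453 | 0.0142 |
| 7 | 2.486 | 0.0129 |

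Only K = 5 returns the plan's pair. That result also supports 5% as the intended overall alpha.

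**Number of looks under each schedule.**
- Every 100 infants: 646/100 = 6.46, so 6 looks, or 7 with a final at 646.
- Every 160 infants: 646/160 = 4.04, so 4 looks, or 5 with a final at 646, only 6 infants after the look at 640.
- Every 9 months: 48/9 = 5.3, so 5 looks over 48 months; 41/9 = 4.6, so 4 looks over 41 months.

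**Can the schedules coincide?** Enrollment runs from 22 × 0.60 = 13.2 to 25 × 0.70 = 17.5 infants per month.
- 100 infants take 100/17.5 = 5.7 to 100/13.2 = 7.6 months, never 9.
- 160 infants take 160/17.5 = 9.1 to 160/13.2 = 12.1 months, which is near 9 only at the fastest accrual.
- At the planned 48 months, 646/48 = 13.5 infants per month, so 9 months is about 121 infants and matches neither step.

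The lag from enrollment to status (up to 60 days) delays every look by a similar amount. It does not turn a step of 100 into a step of 160.

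**Overall error with 2.413 kept, and the constant needed for 5%.** Information is taken as proportional to infants (or to months, for the calendar schedule). Results are per outcome.

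| Looks at | Overall error at 2.413 | Constant for 5% (nominal p) |
|---|---|---|
| 100, …, 600 | 5.5% | 2.453 (0.0142) |
| 100, …, 600, 646 | 5.8% | 2.475 (0.0133) |
| 160, …, 640 | 4.4% | 2.361 (0.0182) |
| 160, …, 640, 646 | 4.5% | 2.371 (0.0177) |
| months 9, …, 45 (5 equal looks) | 5.0% | 2.413 (0.0158) |
| months 9, …, 45, 48 | 5.3% | 2.436 (0.0148) |
| months 9, …, 36 | 4.4% | 2.361 (0.0182) |
| months 9, …, 36, 41 | 4.85% | 2.401 (0.0163) |

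**If the sample size is recalculated.** Taking 800 purely as an illustration, looks every 100 infants (8 looks) give 6.4% at 2.413, and looks every 160 (5 looks) give 5.0%.

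**The case against.** The best defense is that the boundary is attached to the clause about 9 months and 160 infants, not to the 100-infant clause. Four looks at steps of 160 plus a final make five, as do five 9-monthly looks over 48 months, and under those readings 2.413 is adequate or slightly conservative. This is a plausible account of where the number came from. It does not rescue the text: the sentence that says what the DSMC will do uses steps of 100, and a reader cannot tell that it should be set aside.

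A second argument is that the inflation may not appear in practice. The integration assumes normal statistics, the outcomes are binary with about 50 infants per arm at the first look, and no test is named. Simulation of the 100-infant rule with six looks and an uncorrected z-test gave 3.7% at an assumed event rate of 3% and 5.4% at 10%; Fisher's exact test stayed below 5%. That stands as a qualification: the 5.5% applies to an approximately normal statistic and event rates near 10% or more. It does not settle which schedule the boundary serves.

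Third, a lenient harm boundary errs toward flagging harm early, the Chair hears of any suspected trend, and efficacy has its own O'Brien-Fleming bounds. All of this is true, and it limits the consequence. A sponsor may choose a lenient safety boundary, but the plan should then say so. The full-committee meetings at 50% and 75% only circulate the reports and do not define another boundary.

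**Conclusion.** The concern holds. The constant and its p-value are correct for five equally spaced looks, a number the plan never states. They do not fit the 100-infant rule, and the 100-infant, 160-infant and 9-month statements cannot all be true at any accrual rate the protocol allows. Under the rule as stated, the overall error per outcome is 5.5% (5.8% with a final at 646) against an assumed 5%; under the 160-infant schedule it is 4.4% to 4.5%. These figures rest on the assumed two-sided 5%, on information proportional to infants, and on approximately normal test statistics.

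The numerical effect is modest. The larger problem is that the schedule is undefined. The mismatch under the 100-infant rule would grow if the planned recalculation raised the sample size. This should be corrected, but it does not threaten the primary analysis.

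**What to change.** Rewrite the interim safety monitoring paragraph to state one schedule, one clock (infants reaching status or infants enrolled), the overall safety alpha, the number of looks, the test statistic, and whether a final analysis counts. Then print the constant that follows. At an overall two-sided 5%:

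- every 100 infants: 2.453 (p<0.0142), or 2.475 (p<0.0133) with a final at 646;
- every 160 infants: 2.361 (p<0.0182), or 2.371 (p<0.0177) with a final at 646;
- five equal looks, about every 646/5 = 129 infants: keep 2.413 (p<0.0158).

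Alternatively, use a Lan-DeMets Pocock-type spending function indexed to infants reaching status. It holds the chosen alpha whatever the number of looks and can accommodate the sample size recalculation planned below Table 10. Whichever is chosen, remove or align the other interval statements. The cost is one paragraph and the DSMC report template, with no additional patients.

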## Nomenclature

ACTH	adrenocorticotropic hormone
ARDS	acute respiratory distress syndrome
BP	blood pressure
BSID	Bayley Scales of Infant Development
CLD	chronic lung disease
CRH	corticotrophin-releasing hormone
CT	computed axial tomography
DSMC	Data Safety and Monitoring Committee
ECMO	extracorporeal membrane oxygenation
GA	gestational age
GMF	gross motor function
HPA	hypothalamic-pituitary-adrenal
HUS	head ultrasound
IVH	intraventricular hemorrhage
NEC	necrotizing enterocolitis
NICU	newborn intensive care unit
NRN	Neonatal Research Network
PMA	postmenstrual age
PVL	periventricular leukomalacia
RCT	randomized controlled trial
SD	standard deviation
SIP	spontaneous intestinal perforation

